15.0 DATA HANDLING, DATA MANAGEMENT, RECORD KEEPING

15.1 Source Documents

Source documents are original documents, data, and records (e.g., medical records, pharmacy dispensing records, recorded data from automated instruments, laboratory data) that are relevant to the clinical trial. The Site Investigator or their designee will prepare and maintain adequate and accurate source documents. These documents are designed to record all observations and other pertinent data for each patient enrolled in this clinical trial. Source documents must be adequate to reconstruct all data transcribed onto the case report forms.

15.2 Data Capture Methods and Management

Data for this trial will be collected using Medidata RAVE, City of Hope's electronic capture system. Medidata RAVE is a web based, password protected system that is fully compliant with global regulatory requirements, including 21CRF Part 11 compliant.

15.3 Case Report Forms/ Data Submission Schedule

Study personnel at each site will enter data from source documents corresponding to a participant's visit into the protocol-specific electronic Case Report Form (eCRF) when the information corresponding to that visit is available.

The investigator is responsible for all information collected on participants enrolled in this study. All data collected during the course of this study must be reviewed and verified for completeness and accuracy by the investigator. All case report forms must be completed by designated study personnel. The completed case report forms must be reviewed, signed and dated by the Site Investigator or designee in a timely fashion.

All data will be collected using electronic data collection system described in Section 15.2, and will be submitted according to the timelines indicated in Table 14.

Table 14. Data Submission Schedule

Form	Submission Timeline
Eligibility Checklist	Complete prior to registration
On Study Forms	Within 14 calendar days of registration
Baseline Assessment Forms	Within 14 calendar days of registration
Treatment Forms	Within 14 calendar days of treatment administration
Adverse Event Report Forms	Cycle 1 and 2: Within 7 calendar days of the assessment/notification Cycle 3+: Within 10 calendar days of the assessment/notification
Response Assessment Forms	Within 10 calendar days of the response assessment
Other Assessment Forms	Within 10 calendar days of the assessment

Form	Submission Timeline
Off Treatment/Off Study Forms	Within 10 calendar days of completing treatment or being taken off study for any reason
Follow up/ Survival Forms	Within 14 calendar days of the protocol defined follow up visit date or call

15.4 Regulatory Records

The investigator will maintain regulatory records, including updating records in accordance with Good Clinical Practice guidelines and FDA regulations.

16.0 ADHERENCE TO THE PROTOCOL

A deviation is a divergence from a specific element of a protocol that occurred without prior IRB approval.

It is understood that deviations from the protocol should be avoided, except when necessary to eliminate an immediate hazard to a research participant. Protocol deviations may be on the part of the participant, the investigator, or study staff.

All deviations from the protocol must be documented in study participant source documents and promptly reported to the Study PI and to the local IRB according to its policies requirements. The Study PI will report the deviation according to City of Hope's deviation policy for reporting deviations.

16.1 Definitions

16.1.1 Unplanned deviations

- **Emergency Modifications**

Investigators may implement a deviation from the protocol to eliminate an immediate hazard(s) for the protection, safety, and well-being of the study patient to trial participants without prior IRB or Sponsor approval.

- **Deviations Discovered After They Have Occurred**

Unplanned deviations from the protocol must be documented in study subject source documents.

16.1.2 Planned Non-Emergency Deviations (Single Subject Exception)

A planned deviation involves circumstances in which the specific procedures called for in a protocol are not in the best interests of a specific patient. It is a deviation that is anticipated and receives prior approval by the PI and the IRB.

16.2 Reporting of Deviations

16.2.1 Reporting Unplanned Deviations

For any such deviation, the Study PI will notify the COH DSMC and IRB within 5 calendar days of its occurrence via [iRIS](#) in accordance with the [Clinical Research Protocol Deviation policy](#).

A list of these deviations will be submitted along with the Protocol Management Team (PMT) reports to the COH DSMC.

16.2.2 Reporting Planned Non-Emergency Deviations/ Single Subject Exceptions

Any planned deviation must be submitted as a “planned protocol deviation” via [iRIS](#) in accordance with IRB guidelines and the [Clinical Research Protocol Deviation policy](#). An IRB approved planned deviation does not need to be submitted as a deviation to the DSMC.

17.0 ETHICAL AND REGULATORY CONSIDERATIONS

17.1 Ethical Standard

This study will be conducted in conformance with the principles set forth in The Belmont Report: Ethical Principles and Guidelines for the Protection of Human Subjects of Research (US National Commission for the Protection of Human Subjects of Biomedical and Behavioral Research, April 18, 1979) and the Declaration of Helsinki.

17.2 Regulatory Compliance

This study is to be conducted in compliance with the IRB approved protocol and according to the following considerations:

- US Code of Federal Regulations (CFR) governing clinical study conduct
 - Title 21 Part 11 – Electronic Records; Electronic Signatures
 - Title 21 Part 50 – Protection of Human Subjects
 - Title 21 Part 54 – Financial Disclosure by Clinical Investigators
 - Title 21 Part 56 – Institutional Review Boards
 - Title 21 Part 58 – Good Laboratory Practice for Nonclinical Laboratory Studies
 - Title 21 Part 312 – Investigational New Drug Application
 - Title 45 Part 46 – Protection of Human Subjects
- US Federal legislation, including but not limited to
 - Health Insurance Portability and Accountability Act of 1996
 - Section 801 of the Food and Drug Administration Amendments Act

- Applicable state and local laws. For research occurring in California, this includes but is not limited to State of California Health and Safety Code, Title 17
- Applicable institutional research policies and procedures

17.3 Institutional Review Board

An Institutional Review Board (IRB) that complies with the federal regulations at 45 CFR 46 and 21 CFR 50, 56 and State of California Health and Safety code, Title 17, must review and approve this protocol, informed consent form and any additional documents that the IRB may need to fulfill its responsibilities (Investigator's Brochure, information concerning patient recruitment, payment or compensation procedures, or other pertinent information) prior to initiation of the study. Revisions to approved documents will require review and approval by the IRB before the changes are implemented in the study. All institutional, NCI, Federal, and State of California regulations must be fulfilled.

The IRB's written unconditional approval of the study protocol and the informed consent document must be in the possession of the investigator before the study is initiated.

The IRB will be informed of serious unexpected, unanticipated adverse experiences, and unanticipated problems occurring during the study, and any additional adverse experiences in accordance with the standard operating procedures and policies of the IRB; new information that may affect adversely the safety of the patients of the conduct of the study; an annual update and/or request for re-approval; and when the study has been completed.

17.4 Informed Consent

The Principal Investigator or IRB approved named designee will explain the nature, duration, purpose of the study, potential risks, alternatives and potential benefits, and all other information contained in the informed consent document. In addition, they will review the experimental subject's bill of rights if applicable, and the HIPAA research authorization form. Prospective participants will be informed that they may withdraw from the study at any time and for any reason without prejudice, including as applicable, their current or future care or employment at City of Hope or any relationship they have with City of Hope. Prospective participants will be afforded sufficient time to consider whether or not to participate in the research.

After the study has been fully explained, written informed consent will be obtained from either the prospective participant or his/her guardian or legal representative before study participation. The method of obtaining and documenting the informed consent and the contents of the consent must comply with the ICH-GCP and all applicable regulatory requirements.

A copy of the signed informed consent will be given to the participant or his/her legally authorized representative. The original signed consent must be maintained by the investigator and available for inspection by sponsor designated representatives, or regulatory authority at any time.

Informed consent is a process that is initiated prior to the individual agreeing to participate in the study and continues throughout study participation.

17.5 Participant Withdrawal

Participants may withdraw from the study at any time and for any reason without prejudice. The withdrawal must be documented per institutional policies.

Participant withdrawal may consist of any of the following with regard to study procedures and data collection:

- Withdrawal from study treatment, but agreement to continue with active study procedures and chart review and follow-up procedures.
- Withdrawal from study treatment and all active procedures, but agreement for chart review and follow-up procedures.
- Withdrawal from study treatment, all active procedures, and any future data collection.

Participants who agreed to the collection of research blood samples may withdraw consent to use their specimens, if they are not yet processed as detailed in the consent form. Once the PI and site PI is notified of this withdrawal of informed consent, the research specimens will not be used in any research. At that time, any of the existing specimens will be destroyed.

17.6 Special and Vulnerable Populations

17.6.1 Inclusion of Women and Minorities

The study is open anyone regardless of gender or ethnicity. If differences in outcome that correlate to gender, racial, or ethnic identity are noted, accrual may be expanded or additional studies may be performed to investigate those differences more fully.

Pregnant women are excluded from the study. Animal reproduction studies have not been conducted, and there are no controlled data in human pregnancy.

Therefore, vorinostat and pembrolizumab should not be taken by pregnant women.

17.6.2 Exclusion of Children

Children/ adolescents (< 18 years old of age) are excluded from this study because the historical comparator trials were conducted in adults. Future studies may be planned to include children/ adolescents.

17.6.3 Inclusion of HIV Positive Individuals

Participants with a history of HIV are excluded due to concerns about inadvertent augmentation of infectious and/or inflammatory activity.

17.6.4 Vulnerable Populations

45 CFR §46.111 (a)(3) and 45 CFR §46, Subparts B-D identifies children, prisoners, pregnant women, mentally incapacitated persons, or economically or educationally disadvantaged persons as vulnerable populations.

Adults lacking capacity to consent are not excluded from participation. This study does not pose additional risks for adults lacking capacity than for the general population. In such instances, informed consent will be sought and documented from the prospective participant's legally authorized representative in agreement with institutional policies and COH IRB approval.

17.7 Participant Confidentiality

Participant confidentiality is strictly held in trust by the investigators, study staff, and the sponsor(s) and their agents. This confidentiality is extended to cover testing of biological samples in addition to any study information relating to participants.

This research will be conducted in compliance with federal and state requirements relating to protected health information (PHI), including the requirements of the Health Insurance Portability and Accountability Act of 1996 (HIPAA). HIPAA regulations require a signed participant authorization informing the participant of the nature of the PHI to be collected, who will have access to that information and why, who will use or disclose that information, and the rights of a research participant to revoke their authorization for use of their PHI. In the event that a participant revokes authorization to collect or use PHI, the investigator, by regulation, retains the ability to use all information collected prior to the revocation of participant authorization. For participants that have revoked authorization to collect or use PHI, attempts should be made to obtain permission to collect at least vital status (i.e. that the participant is alive) at the end of their scheduled study period.

Release of research results should preserve the privacy of medical information and must be carried out in accordance with Department of Health and Human Services Standards for Privacy of Individually Identifiable Health Information, 45 CFR 164.508. When results of this study are reported in medical journals or at meetings, identification of those taking part will not be disclosed and no identifiers will be used.

Medical records of participants will be securely maintained in the strictest confidence, according to current legal requirements. Data will be entered, analyzed and stored in encrypted, password protected, secure computers that meet all HIPAA requirements. All data capture records, drug accountability records, study reports and communications will identify the patient by initials and the assigned patient number. Source documents provided to coordinating center for the purpose of auditing or monitoring will be de-identified and labeled with the study number, subject ID, and if applicable patient initials.

The investigator/institution will permit direct access to source data and documents by sponsor representatives, the FDA, and other applicable regulatory authorities. The access may consist of trial-related monitoring/ auditing, IRB reviews, and FDA/regulatory authority inspections. The participant's confidentiality will be maintained and will not be made publicly available to the extent permitted by the applicable laws and regulations.

Participant specimens will be de-identified (coded) prior to submission to research laboratories. The specimens will be labeled with the study number, subject ID, institution and

timepoint of collection. The key to the code will be maintained in the COH clinical trials management system which is a secure environment.

17.8 Use of Unused (Leftover) Specimens Collected for this Trial

Unused samples in existence at study completion (i.e. completion of all research activities under this study) will be either: (a) discarded or (b) placed in a COH IRB approved biorepository with clinical information and potentially PHI attached.

With regard to which option will apply, each site IRB may choose to either: (a) leave the determination to the participant via a question in the informed consent document, which would be communicated to the study registrar (DCC) at the time of participant registration, OR b) may choose to make a single determination on behalf of their respective participants, and communicate that determination to their respective participants via the informed consent.

17.9 Conflict of Interest

Any investigator who has a conflict of interest with this study (patent ownership, royalties, or financial gain greater than the minimum allowable by their institution, etc.) must have the conflict reviewed by a properly constituted Conflict of Interest Committee with a Committee-sanctioned conflict management plan that has been reviewed and approved by the study Sponsor (City of Hope) prior to participation in this study. All City of Hope investigators will follow the City of Hope conflict of interest policy.

All study personnel are required to disclose financial interests in the company involved with this study, Merck.

17.10 Financial Obligations, Compensation, and Reimbursement of Participants

The investigational drugs, pembrolizumab and vorinostat, will be provided free of charge by Merck. Should pembrolizumab become commercially available during the course of study treatment, the research participant and/or the insurance carrier may be asked to pay for the costs of the drug.

Neither the research participant nor the insurance carrier will be responsible for the research procedures related to this study.

The standard of care drugs and procedures provided will be the responsibility of the research participant and/or the insurance carrier. The research participant will be responsible for all copayments, deductibles, and other costs of treatment and diagnostic procedures as set forth by the insurance carrier. The research participant and/or the insurance carrier will be billed for the costs of treatment and diagnostic procedures in the same way as if the research participant were not in a research study.

In the event of physical injury to a research participant, resulting from research procedures, appropriate medical treatment will be available at the City of Hope or at the non-COH site to the injured research participant, however, financial compensation will not be available. There are no plans for City of Hope to provide financial compensation in the event of physical injury to a participant.

The research participant will not receive reimbursement or payment for taking part in this study.

17.11 Publication/Data Sharing

Neither the complete nor any part of the results of the study carried out under this protocol, nor any of the information provided by City of Hope for the purposes of performing the study, will be published or passed on to any third party without the written approval of the Study PI. Any investigator involved with this study is obligated to provide City of Hope with complete test results and all data derived from the study.

The preparation and submittal for publication of manuscripts containing the study results shall be in accordance with a process determined by mutual written agreement among City of Hope and Merck. The publication or presentation of any study results shall comply with all applicable privacy laws, including, but not limited to, the Health Insurance Portability and Accountability Act of 1996.

In accordance with the [U.S. Public Law 110-85](#) (Food and Drug Administration Amendments Act of 2007 or FDAAA), Title VIII, Section 801, this trial will be registered onto [ClinicalTrials.gov](#) and results will be reported on ClinicalTrials.gov within 12 months of the estimated or actual completion date of the trial, whichever date is earlier.

APPENDIX A: ECOG PERFORMANCE STATUS

ECOG Performance Status Scale ¹⁴⁰	
Grade	Descriptions
0	Normal activity. Fully active, able to carry on all pre-disease performance without restriction.
1	Symptoms, but ambulatory. Restricted in physically strenuous activity, but ambulatory and able to carry out work of a light or sedentary nature (e.g., light housework, office work).
2	In bed <50% of the time. Ambulatory and capable of all self-care, but unable to carry out any work activities. Up and about more than 50% of waking hours.
3	In bed >50% of the time. Capable of only limited self-care, confined to bed or chair more than 50% of waking hours.
4	100% bedridden. Completely disabled. Cannot carry on any self-care. Totally confined to bed or chair.
5	Dead.

APPENDIX B: REGISTRATION COVERSHEET

COH IRB#: A Phase I Study of Pembrolizumab Plus Vorinostat for Relapsed or Refractory Diffuse Large B-cell Lymphoma, Follicular Lymphoma, and Hodgkin Lymphoma

Data Coordinating Center:

City of Hope
 [name]
 [name]
 Email: [contact] (use #secure# in subject line)

Site Principal Investigator

Name:
 Address:

Phone:
 Fax:
 e-mail:

CRA/Study Coordinator:	Contact Number:
Patient's Initials: (F M L):	Institution:
Medical Record No.:	Investigator/Treating Physician:
Patient's DOB:	IRB approval valid until (date):
Sex: _____ Male _____ Female	Date Informed Consent Signed:
	Projected start date of treatment:

Race		Ethnicity		Method of Payment: _____
	Black		Hispanic	Codes: _____
	Caucasian		Non-Hispanic	01 Private 06 Military or Veterans Adm. sponsored
	Asian		Other _____	02 Medicare 07 Self-pay (no insurance)
	American Indian			03 Medicare & private ins. 08 No means of payment (no insurance)
	Native Hawaiian/Pacific Islander			04 Medicaid 09 Unknown
	Other _____			05 Medicaid & Medicare

Reason for Screen Failure:

Reason for Failing to Initiate Protocol Therapy:

APPENDIX C: THE 2014 LUGANO CLASSIFICATION

The 2014 Lugano Classification will be used in this study for assessment of tumor response. PET/CT will be used for HL and DLBCL, and is acceptable for FL, while CT with IV contrast (or MRI) can be used for FL.

Response	Site	CT-Based Response	PET-CT Based Response
Complete Response	Lymph nodes and extralymphatic sites	Complete radiologic response (all of the following) 
 Target nodes/nodal masses must regress to ≤ 1.5 cm in longest diameter. No extralymphatic sites of disease. 	Complete metabolic response (even with a persistent mass) 
 Score $\leq 3^*$ with or without a residual mass on 5-point scale†. It is recognized that in Waldeyer's ring or extranodal sites with high physiologic uptake or with activation within spleen or marrow (e.g., with chemotherapy or myeloid colony-stimulating factors), uptake may be greater than normal mediastinum and/or liver. In this circumstance, complete metabolic response may be inferred if uptake at sites of initial involvement is no greater than surrounding normal tissue even if the tissue has high physiologic uptake.
	Nonmeasured lesion	Absent	Not applicable
	Organ enlargement	Regress to normal	Not applicable
	New lesions	None	None
	Bone marrow	Normal by morphology; if determinate, IHC negative	No evidence of FDG-avid disease in marrow
Partial Response		Partial remission (all of the following)	Partial metabolic response
	Lymph nodes and extralymphatic sites	
 $\geq 50\%$ decrease in SPD of up to 6 target measurable nodes and extranodal sites When a lesion is too small to measure on CT, assign 5 mm X 5 mm as the default value When no longer visible, 0 X 0 mm For a node > 5 mm X 5 mm, but smaller than normal, use actual measurement for calculation 	
 Score 4 or 5† with reduced uptake compared with baseline and residual mass(es) of any size At interim, these findings suggest responding disease At end of treatment, these findings indicate residual disease

Response	Site	CT-Based Response	PET-CT Based Response
	Nonmeasured lesion	Absent/normal, regressed, but no increase	Not applicable
	Organ enlargement	Spleen must have regressed by > 50% in length beyond normal	Not applicable
	New lesions	None	None
	Bone marrow	Not applicable	Residual uptake higher than uptake in normal marrow but reduced compared with baseline (diffuse uptake compatible with reactive changes from chemotherapy allowed). If there are persistent focal changes in the marrow in the context of a nodal response, consideration should be given to further evaluation with MRI or biopsy or an interval scan
No response or stable disease	Stable disease		No metabolic response
	Target nodes/nodal masses, extranodal lesions	< 50% decrease from baseline in SPD of up to 6 dominant, measurable nodes and extranodal sites; no criteria for progressive disease are met	Score 4 or 5† with no significant change in FDG uptake from baseline at interim or end of treatment
	Nonmeasured lesion	No increase consistent with progression	Not applicable
	Organ enlargement	No increase consistent with progression	Not applicable
	New lesions	None	None
	Bone marrow	Not applicable	No change from baseline
	Progressive disease requires at least 1 of the following		Progressive metabolic disease
Progressive disease	Individual target nodes/nodal masses	PPD progression:	Score 4 or 5 with an increase in intensity of uptake from baseline and/or
	Extranodal lesions	
An individual node/lesion must be abnormal with:
 
 • Longest diameter (LDi) > 1.5 cm and • Increase by ≥ 50% from PPD nadir and • An increase in LDi or smallest diameter (SDi) from nadir • 0.5 cm for lesions ≤ 2 cm • 1.0 cm for lesions > 2 cm 	
 • New FDG-avid foci consistent with lymphoma at interim OR end-of-treatment assessment

Response	Site	CT-Based Response	PET-CT Based Response
		
 In the setting of splenomegaly, the splenic length must increase by > 50% of the extent of its prior increase beyond baseline (e.g., a 15-cm spleen must increase to 16 cm). If no prior splenomegaly, must increase by at least 2 cm from baseline New or recurrent splenomegaly 	
	Nonmeasured lesion	New or clear progression of preexisting nonmeasured lesions	None
	New lesions	
 Regrowth of previously resolved lesions A new node > 1.5 cm in any axis A new extranodal site < 1.0 cm in any axis; if > 1.0 cm in any axis, its presence must be unequivocal and must be attributable to lymphoma Assessable disease of any size unequivocally attributable to lymphoma 	
 New FDG-avid foci consistent with lymphoma rather than another etiology (eg, infection, inflammation). If uncertain regarding etiology of new lesions, biopsy or interval scan may be considered.
	Bone marrow	New or recurrent involvement	New or recurrent FDG-avid foci

Measured dominant lesions:

Up to six of the largest dominant nodes, nodal masses, and extranodal lesions selected to be clearly measurable in two diameters. Nodes should preferably be from disparate regions of the body and should include, where applicable, mediastinal and retroperitoneal areas.

Non-nodal lesions include those in solid organs (e.g., liver, spleen, kidneys, lungs), GI involvement, cutaneous lesions, or those noted on palpation.

Nonmeasured lesions:

Any disease not selected as measured, dominant disease and truly assessable disease should be considered not measured. These sites include any nodes, nodal masses, and extranodal sites not selected as dominant or measurable or that do not meet the requirements for measurability but are still considered abnormal, as well as truly assessable disease, which is any site of suspected disease that would be difficult to follow quantitatively with measurement, including pleural effusions, ascites, bone lesions, leptomeningeal disease, abdominal masses, and other lesions that cannot be confirmed and followed by imaging. In Waldeyer's ring or in extranodal sites (e.g., GI tract, liver, bone marrow), FDG uptake may be greater than in the mediastinum with complete metabolic response, but should be no higher than surrounding normal physiologic uptake (eg, with marrow activation as a result of chemotherapy or myeloid growth factors).

*A score of 3 in many patients indicates a good prognosis with standard treatment, especially if at the time of an interim scan. However, in trials involving PET where de-escalation is investigated, it may be preferable to consider a score of 3 as inadequate response (to avoid undertreatment).

†*PET 5-point score:*

1, no uptake above background; 2, uptake \leq mediastinum; 3, uptake $>$ mediastinum but \leq liver; 4, uptake moderately $>$ liver; 5, uptake markedly higher than liver and/or new lesions; X, new areas of uptake unlikely to be related to lymphoma.

Abbreviations:

CT, computed tomography; FDG, fluorodeoxyglucose; IHC, immunohistochemistry; LD_i, longest transverse diameter of a lesion; MRI, magnetic resonance imaging; PET, positron emission tomography; PPD, cross product of the LD_i and perpendicular diameter; SD_i, shortest axis perpendicular to the LD_i; SPD, sum of the product of the perpendicular diameters for multiple lesions.

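### Appendix C reverses the two size signs for a new extranodal site on CT, so an equivocal site under 1.0 cm is progression by itself and can date DOR and PFS events too early

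*Combined protocol and SAP*

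**What the plan says.** Sections 9.2.6 and 10.1 base response and progression on the 2014 Lugano Classification and point to Appendix C for it. In the CT column of that table the governing condition is "Progressive disease requires at least 1 of the following". The New lesions cell of that column then lists "A new extranodal site < 1.0 cm in any axis; if > 1.0 cm in any axis, its presence must be unequivocal", and goes on to require that it be due to lymphoma. The same cell lists "A new node > 1.5 cm in any axis" and "Assessable disease of any size unequivocally attributable to lymphoma".

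The row above makes this progression too: "New or clear progression of preexisting nonmeasured lesions". The notes under the table define nonmeasured lesions to include sites "or that do not meet the requirements for measurability but are still considered abnormal".

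Section 10.2 ends DOR at progression and PFS at first progression, relapse or death. Both are secondary endpoints. Section 11.1.3 estimates them by Kaplan-Meier, separately for DLBCL, FL and HL.

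**The concern.** As printed, the smaller the site, the less proof it needs. A new extranodal spot under 1.0 cm carries no condition of certainty or cause, while one over 1.0 cm must be definite and due to lymphoma. A size threshold in a progression rule normally works the other way, because small findings are the doubtful ones.

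This matters more than usual with a checkpoint inhibitor. Section 4.4.6 lists pneumonitis and sarcoidosis among the expected toxicities of pembrolizumab, so small new lesions that are not lymphoma are plausible. At stake are the progression dates behind DOR and PFS. PFS is also an outcome in the exploratory biomarker and PET analyses of section 11.4.

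**Working it through.** No sample size, power or event figure depends on this line, so the plan has no number to reproduce. The check is one of logic, followed by the scale of one error.

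**1. Is the line reversed?** Two comparisons within the table say so.
- The CT rules for nodes and existing lesions set a floor: "Longest diameter (LDi) > 1.5 cm and" for an existing node or lesion, and more than 1.5 cm for a new node. Only the extranodal line sets a ceiling.
- The PET-CT cell of the same row asks for cause: "New FDG-avid foci consistent with lymphoma rather than another etiology (eg, infection, inflammation". The printed CT line asks nothing about cause for a site under 1.0 cm.

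The any-size bullet is weaker evidence. It makes the demand for certainty redundant under either order of the signs. What it does show is that the size line changes a decision only for equivocal sites.

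**2. Which cases change?**

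| New extranodal site on CT | Printed bullet | Signs exchanged |
|---|---|---|
| < 1.0 cm, equivocal | PD | not PD |
| < 1.0 cm, unequivocal lymphoma | PD | PD |
| > 1.0 cm, equivocal | not PD by this bullet | PD |
| > 1.0 cm, unequivocal lymphoma | PD | PD |

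A site of exactly 1.0 cm falls under neither sign. The nonmeasured-lesion row may override some of these cells:
- If it does not reach equivocal new sites, 2 of 4 cases differ.
- If it catches equivocal sites > 1.0 cm only, 1 of 4 differs: the false PD below 1.0 cm.
- If it catches every suspected site of any size, 0 of 4 differ, but then the size limits for new lesions would have no function.

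**3. Which scans are exposed?** Only CT-read ones. Section 10.1 allows CT for FL at any time point. For HL and DLBCL it requires PET-CT at baseline, at cycle 4 and to confirm CR; at other times CT may be used. FL is closed to enrolment (section 5.1.1), so exposed FL patients are among the first 42 (section 4.6.4). The remaining 52 − 42 = 10 patients (10/52 = 19%) are HL.

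**4. How large is one false call?**
- Timing: staging every 4 cycles is 4 × 21 = 84 days (12 weeks). After the first follow-up year it is 18 × 7 = 126 days (section 9.5.3.4). If true progression is first seen on the next scheduled scan, the date is early by that much; if later, by more.
- Height of the curve: with no earlier event, one event among n at risk lowers a Kaplan-Meier curve by 1/n. For assumed n = 5, 10 and 20 that is 20, 10 and 5 points. For scale only, the 13 responders in section 4.6.4 give 1/13 = 7.7 points.

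**5. Illustration on assumed rates.** Let m be the true median PFS in weeks and f the probability of a false PD per CT scan; neither is in the documents. With CT at every 12-week scan, S(48) = [0.5^(12/m) × (1 − f)]^4. If the first scan is PET-CT, the power on (1 − f) is 3. For m = 52: 0.5^(48/52) = 0.5274; × 0.99^4 (0.9606) = 0.507; × 0.95^4 (0.8145) = 0.430.

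| m (weeks) | True 48-week PFS | CT at every scan, f = 1% to 5% | CT after cycle 4 only, f = 1% to 5% |
|---|---|---|---|
| 26 | 27.8% | 26.7% to 22.7% | 27.0% to 23.8% |
| 52 | 52.7% | 50.7% to 43.0% | 51.2% to 45.2% |
| 104 | 72.6% | 69.8% to 59.2% | 70.5% to 62.3% |

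The illustration covers the false-PD direction only, so it is not an estimate of net bias.

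**The case against.** The best reply is that this is a transcription slip with no demonstrated effect. The standard that the protocol names is the 2014 Lugano Classification; section 11.1.3 cites it without mentioning Appendix C, and readers who know it may already apply the sensible rule. Progression is checked in other ways: a recommended biopsy (sections 9.2.6 and 10.1), image quality assurance by the study PI (section 13.6), and LYRIC, under which a new lesion with limited overall growth leads to repeat imaging. DOR and PFS are preliminary estimates with no test attached.

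Much of that stands. Nothing shows that anyone applied the printed sign, and the endpoints are secondary. But Appendix C is the only place where the protocol spells the rule out, and sections 9.2.6 and 10.1 send the assessor there. The biopsy is optional, the image review has no stated criterion that would correct this line, and LYRIC is applied after Lugano progression. None of them redefines the Lugano progression date.

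A reader might infer more than the documents support:
- *That DOR and PFS are biased by a known amount, or that recorded dates are wrong.* The number of FL patients, the number of CT-read scans and the rate of equivocal new sites are not given.
- *That the line equally delays progression for equivocal sites over 1.0 cm.* This is possible, but the nonmeasured-lesion row may catch them.
- *That every HL and DLBCL scan after cycle 4 is exposed.* PET-CT is still required to confirm CR, and the opening of Appendix C expects PET-CT in these diseases.
- *That later scans will usually expose a wrong date.* Staging runs until progression, and treatment past progression is discretionary (section 9.2.6.1).

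**Conclusion.** The line is wrong as written and should be corrected. The firmer consequence is a false early progression date when an equivocal new extranodal site under 1.0 cm is read on CT; the opposite error is less certain. That consequence rests on two assumptions: that assessors follow the printed text, and that the nonmeasured-lesion row does not already make every suspected new site progression.

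One false call is worth at least 12 or 18 weeks of time if true progression shows no earlier than the next scheduled scan, and 1/n on the curve if it is the first event. Overall size and net direction cannot be derived. ORR is little exposed, because section 10.2 counts a response at any time on treatment. The primary toxicity endpoint, DLT, MTD/RP2D and the stopping rule do not use this rule.

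**What to change.** Exchange the two signs, so that a new extranodal site > 1.0 cm counts by size and one < 1.0 cm counts only if it is unequivocal and attributable to lymphoma. Assign exactly 1.0 cm to one side.

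Before the efficacy analysis, list the CT-based progression calls that rested solely on a new extranodal site and check each against the corrected rule. Use the report of that same scan, not later scans, biopsies or outcomes: in an open-label trial, re-dating with hindsight invites outcome-driven changes. Leave the section 10.2 censoring rules as they are, and report how many calls change. This check does not look for the opposite error, which is the less certain one.

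The cost is a one-line correction and a small amount of record review. It needs no new imaging and no change to treatment or sample size.
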